1.2.19. Assessment of the Drug-Drug Interaction (DDI) Potential between Glasdegib and Azacitidine

Glasdegib has been shown to be extensively metabolized by CYP3A4 (99.8%) using human liver microsomes and hepatocytes. For azacitidine, the exact route of elimination and metabolic fate is not known in humans. One of the pathways of elimination for azacitidine appears to be deamination by cytidine deaminase principally located in the liver but also in granulocytes, the intestinal epithelium, and whole blood (Vidaza® US package insert). The potential for a DDI was considered to be low for the glasdegib and azacitidine, as enzyme systems other than CYP3A may be involved in the metabolism of azacitidine. However, since this was a combination setting for dosing of glasdegib and azacitidine, a DDI assessment was conducted in twelve subjects as part of the safety LIC. Based on preliminary PK results, there was no evidence of changes in the PKs of either glasdegib or azacitidine when dosed in combination as compared to single agent dosing.

1.2.20. Summary of Benefit-Risk Assessment

An evaluation of the anticipated risks and benefits of treatment with glasdegib in the defined patient population as required in Article 3(2)(a) of Directive 2001/20/EC (cf. Article 6(3)(b) of Directive 2001/20/EC) has been conducted.

Based on the available clinical data, the safety profile of glasdegib as a single agent and in combination administered orally on a once daily continuous dosing regimen is characterized by manageable and potentially reversible toxicities that are generally mild to moderate in severity. The key observed toxicities are: muscle spasms, dysgeusia, decreased appetite, and alopecia.

Small but significant increases in the QTc interval have been reported in non-clinical studies with glasdegib. Across the clinical program at glasdegib doses of 100 mg QD, cases of QTcF prolongation >500 msec or change in QTcF >60 msec from baseline have been reported, generally in settings of multiple confounders; causal relationship could not be determined. Specific dosing modification and additional monitoring may apply in case of prolonged QTcF (refer to [Section 5.4.5.1](#) and [Table 14](#)). Concomitant administration of glasdegib with moderate/strong CYP3A4/5 inhibitors ([Appendix 6](#) and [Appendix 7](#)) and drugs with known risk of Torsade de Pointes (TdP) ([Appendix 5](#)) is not recommended due to the potential for DDI to prolong the QTc interval.

In a thorough QT (TQT) study (Study B1371023), a large effect (≥ 20 msec, the threshold of clinical concern for cancer drugs) of glasdegib on the QTc interval was not demonstrated at therapeutic (exposure equivalent to 100 mg QD) and suprathematic (exposure equivalent to 200 mg QD) doses. The largest mean QTc interval change at any time point following the therapeutic dose was 8.03 msec. The upper bound of the 2-sided 90% CIs for all time-matched least squares (LS) mean differences between glasdegib and placebo was below 20 msec (the maximum 90% CI upper bound was 15.6 msec at the suprathematic dose). Based on PK-PD analysis in cancer patients, there was no observed relationship between glasdegib concentration and heart rate. The predicted mean change in QT interval corrected for heart rate using Fridericia's formula (QTcF) from baseline was 5.30 msec (95% CI: 4.40, 6.24) at the mean C_{max} at the therapeutic dose of 100 mg QD, and 12.1 msec (95% CI: 10.0,

14.3) at the mean supratherapeutic C_{max} . The upper bound of the 95% CI for the projected increases in QTcF were below 20 msec.

When glasdegib was combined with treatments commonly used in patients with higher risk MDS and AML who were not candidates for intensive chemotherapy (azacitidine, decitabine, and LDAC), improvements in response rates and OS in the context of historical controls were observed.

Azacitidine has been shown to prolong OS in patients with higher risk MDS¹⁸ with an acceptable safety profile, but following treatment failure, life expectancy is short, with a mOS of <6 months. In AML patients who were not candidates for intensive chemotherapy, azacitidine has demonstrated a clinically meaningful survival benefit. Therefore, taken together with clinical and pre-clinical data suggesting a potential relevant role for the Hh pathway in myeloid malignancies, these data support the evaluation of glasdegib in combination with azacitidine in the described therapeutic setting to improve clinical outcomes with respect to treatment with single agent azacitidine.

2. STUDY OBJECTIVES AND ENDPOINTS

2.1. Objectives for the Safety Lead-In Cohort

Primary Objective

- To assess the safety and tolerability of glasdegib when administered in combination with azacitidine in patients with previously untreated Intermediate-2 or High-Risk MDS, AML with 20-30% blasts and multi-lineage dysplasia, and CMML.

Secondary Objectives

- To assess the Response Rate (RR);
- To assess other clinical efficacy measures;
- To characterize the PK of glasdegib and azacitidine alone and in combination;
- To characterize the effects of glasdegib in combination with azacitidine on QTc interval.

CCI

█ [REDACTED]

█ [REDACTED]

█ [REDACTED]

2.2. Endpoints for the Safety Lead-In Cohort

Primary Endpoint

- Adverse events as characterized by type, frequency, severity (as graded by National Cancer Institute Common Terminology Criteria for Adverse Events (NCI CTCAE) v.4.03), timing, seriousness and relationship to study therapy and laboratory abnormalities as characterized by type, frequency, severity (as graded by NCI CTCAE v.4.03) and timing.

Secondary Endpoints

- RR (percentage of patients achieving CR + PR) as defined by modified IWG criteria (2006) ([Appendix 2](#));
- Other efficacy measures HI, mCR, Cytogenetic Response, and SD as defined by modified IWG criteria (2006) ([Appendix 2](#));
- PK parameters of glasdegib and azacitidine, including but not limited to C_{max} , T_{max} and AUC;
- QTc interval.

CCI [REDACTED]

■ [REDACTED]

■ [REDACTED]

■ [REDACTED]

2.3. Objectives for the Expansion

Primary Objective

- To determine the CR rate of glasdegib when administered in combination with azacitidine in patients with previously untreated Intermediate, High, or Very High risk MDS and AML not suitable for intensive chemotherapy.

Secondary Objectives

- To assess OS;
- To assess other clinical efficacy measures;
- To assess duration of CR;

- To assess time to CR;
- To evaluate the overall safety profile of glasdegib + azacitidine;
- To evaluate the pharmacokinetic parameters of glasdegib;
- To characterize any effects of glasdegib + azacitidine on QTc interval.

CCI [REDACTED]

- [REDACTED]
- [REDACTED]
- [REDACTED]
- [REDACTED]
- [REDACTED]

2.4. Endpoints for the Expansion

Primary Endpoint

- CR rate for MDS patients ([Appendix 2](#)) and AML patients ([Appendix 11](#)).

Secondary Endpoints

- OS;
- For MDS cohort: disease-specific efficacy measures, such as marrow CR (mCR), Partial Remission (PR), Stable Disease (SD), Partial or Complete Cytogenetic Response, and Hematologic Improvement (HI) ([Appendix 2](#));
- For AML cohort: disease-specific efficacy measures, such as CR with Incomplete Hematologic Recovery (CRi), Complete Remission with partial hematologic recovery (CRh), Morphologic Leukemia-Free State (MLFS), PR, and SD ([Appendix 11](#));
- Duration of CR;
- Time to CR;

- Adverse events and laboratory abnormalities as graded by NCI CTCAE v.4.03;
- Pharmacokinetics parameters of glasdegib;
- QTc interval.

CCI

3. STUDY DESIGN

3.1. Study Overview

This multi-center, open-label Phase 1b study is designed to evaluate the safety, efficacy, PK, and PD of glasdegib when combined with azacitidine in patients with previously untreated Higher-Risk MDS, AML, and CMML. The Phase 1b study includes two components: (a) a safety LIC, and (b) an expansion phase with two cohorts.

3.2. Safety Lead-In Cohort

As of 23 September 2015, a safety LIC of 12 patients with previously untreated Intermediate-2 or High-Risk MDS per IPSS (n=7), AML with 20-30% blasts and multi-lineage dysplasia (n=3), erythroleukemia (n=1), and CMML (n=1) were enrolled and received open-label treatment with glasdegib at a starting dose of 100 mg given orally once/day in combination with azacitidine at the starting dose of 75 mg/m²/day given SC for 7 consecutive days every 28 days. An evaluation of the DDI potential between glasdegib and azacitidine was performed. See [Section 7](#) for a detailed description of the study assessments. An internal safety review team reviewed the LIC data after each patient had received at least 4 weeks of treatment and determined that the safety profile of glasdegib in combination with azacitidine in the defined population was consistent with what is expected for glasdegib or azacitidine alone with no unexpected toxicities identified, therefore the combination was deemed acceptable to proceed to the next phase of development.

3.3. Expansion

Patients with previously untreated Intermediate, High, or Very High risk MDS per IPSS-R (n=30) or patients with AML who are not candidates for intensive chemotherapy (n=30) will receive glasdegib 100 mg orally once/day in combination with azacitidine per local label or per the Investigational Product Manual (or SPC). Azacitidine may be administered by SC injection or IV infusion at the starting dose of 75 mg/m²/day for 7 days every 28 days. Alternate dosing schedules to administer the 7 doses to accommodate subject and treatment center availability are allowed.

The attribution of ‘not being candidates’ for intensive chemotherapy will be determined by the Investigator based on the patient’s baseline eligibility, comorbidities and other factors according to 2017 ELN recommendations. The primary objective of the expansion component is to demonstrate that the CR rate of the combination treatment in each patient population is reasonably better than the historical CR rate for azacitidine alone in that population using a Bayesian decision criteria allowing early stopping for futility.

Patients in the expansion MDS and AML cohorts will be enrolled continuously. The CR rate among the MDS and AML patients will be continuously monitored throughout the expansion component. After a certain number of patients have been enrolled in each cohort (Table 8 and Table 9, respectively) and observed for at least 28 weeks for the expansion MDS cohort and 24 weeks for the expansion AML cohort, the Sponsor will conduct a review of the CR rate within each expansion cohort to determine if the minimum number of responses are achieved to continue enrollment into that cohort. If the minimum number of CRs in any group is not achieved, then study enrollment will stop for futility. If the study is stopped for futility, patients on active treatment that are deriving clinical benefit will continue on study treatment until they meet the criteria for discontinuation (Section 3.3.1). The Bayesian prior parameter assumptions for each cohort are based on glasdegib combination study data in the respective populations, while prior assumption for control groups are based on historical control data.⁵⁶

Analysis of specific safety criteria will be performed to evaluate stopping enrollment for a specific cohort when there is at least 70% probability that the toxicity rate of any of the below pre-defined safety events of interest in that cohort is above 25% (Section 9.7.2):

- Treatment-related deaths that occur during study treatment through 28 days following the last dose of any study treatment, or the beginning of another anti-cancer therapy, whichever occurs first.
- Drug-induced liver injury (Hy’s Law cases), confirmed as detailed in Section 8.6.2, that occurs during study treatment through 28 days following the last dose of any study treatment, or the beginning of another anti-cancer therapy, whichever occurs first.

- Grade ≥ 3 non-hematologic treatment-related AEs in the first cycle of treatment that have failed to recover to baseline or \leq Grade 1 within 21 days from when the second cycle is due to start (corresponding to recovery before or/on Day 49 of the first cycle) and required permanent discontinuation of study treatment.
- Grade 4 treatment-related neutropenia ($ANC < 500/mm^3$) lasting ≥ 42 days from the start of cycle 1 in the presence of bone marrow hypoplasia without evidence of active AML or MDS.

A safety event of interest is defined as any of the above deemed related to glasdegib and /or azacitidine as assessed by the investigator. All AEs will be classified according to CTCAE version 4.03.

The safety stopping criteria will be applied within a cohort (AML or MDS) starting when at least 10 patients have completed the required follow-up period (28/24 weeks for MDS/AML respectively) and applied continuously afterwards. Enrollment will continue unless the stopping boundary is crossed (Table 10). The same stopping criteria will be used for the AML and MDS cohorts; however, the two cohorts will be analyzed independently.

Table 8. MDS Efficacy Decision Criteria

# Patients with mature response data (inclusive)	Stop expansion MDS enrollment if there are this many responses total:
1-9	No stop
10-13	≤ 2
14-16	≤ 3
17-20	≤ 4
21-24	≤ 5
25-27	≤ 6
28-29	≤ 7
30	Full enrollment

Table 9. AML Efficacy Decision Criteria

# Patients with mature response data (inclusive)	Stop expansion AML enrollment if there are this many responses total:
1-10	No stop
11-13	0
14-17	≤ 1
18-20	≤ 2
21-23	≤ 3
24-27	≤ 4
28-29	≤ 5
30	Full enrollment

[figure not shown]
Table 10. Safety Decision Criteria

# Patients*	Stop cohort enrollment if there are this many patients with any pre-defined safety events of interest**
1-9	No stopping
10-12	≥4
13-16	≥5
17-20	≥6
21-23	≥7
24-27	≥8
28-30	≥9

*Patients who have completed the required follow-up period (ie, 28/24 weeks for MDS/AML respectively) or patients who have experienced any pre-defined safety events of interest within the required follow-up period will be counted.

**A weak prior of Beta (0.5,0.5) was used in the calculation.

Figure 3. Schematic of Study Design

*MDS patients enrolled in the Safety Lead-In component must have Intermediate-2 or High-Risk disease according to IPSS. MDS patients enrolled in the Expansion component must have Intermediate, High, or Very High risk disease according to IPSS-R.

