9.7. Interim Analyses

9.7.1. Futility Analyses

A Bayesian decision rule (Section 3.3) will be used to continuously monitor CR rate without holding enrollment in the expansion component to allow early stopping of the study for futility. The decision rule is to stop enrollment for a specific expansion cohort if the posterior probability of the CR rate in study treatment is no more than 0.2 higher than historical azacitidine is greater than 95% in an expansion cohort, ie, $\Pr(\text{glasdegib+Aza response} < \text{historical Aza response} + 0.2) > 0.95$. The prior distribution assumptions for the Bayesian model are as follow: for MDS cohort, we assume a prior distribution of Beta(1,6) for the study treatment (based on data from MDS patients accumulated in the safety LIC [1 out of 7 MDS patients achieved CR]), and a prior distribution of Beta(15,75) by discounting historical CR rate by half (AZA 001 trial); for the AML cohort, a prior distribution of Beta(4,4) for the study treatment (based on pooled data on AML patients from the B1371003 study [1 out of 4 AML patients achieved CR] and the LIC [3 out of 4 AML patients achieved CR]), and a prior distribution of Beta(23.5,97) by discounting historical CR rate by half.⁵⁷ The Multic Lean software (Version 2.1.0) developed by MD Anderson Cancer Center is used (https://biostatistics.mdanderson.org/softwaredownload/SingleSoftware.aspx?Software_Id=12), which properly models variability in historical control that is more often than not ignored. Stopping for toxicity is not modeled.

The Bayesian decision rule applies once the minimum number of patients (ie, 10) in each expansion cohort has achieved the required follow-up duration (ie, 28 weeks for the expansion MDS cohort and 24 weeks for the expansion AML cohort). The enrollment to the respective expansion cohort will be stopped if the minimum number of responders in that expansion cohort is not achieved (Table 8 for expansion MDS cohort, and Table 9 for expansion AML cohort in Section 3.3). For instance, if there are no more than 4 responders in the first 17 patients who have achieved 28 weeks follow-up, the enrollment into the expansion MDS cohort should be stopped for futility.

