The Bayesian decision rule applies once the minimum number of patients (i.e., 10) in each expansion cohort has achieved the required follow-up duration (i.e., 28 weeks for the expansion MDS cohort and 24 weeks for the expansion AML cohort). The enrollment to the respective expansion cohort will be stopped if the minimum number of responders in that expansion cohort is not achieved (for expansion MDS cohort, and for expansion AML cohort in Protocol Section 3.3). For instance, if there are no more than 4 responders in the first 17 patients who have achieved 28 weeks follow-up, the enrollment into the expansion MDS cohort should be stopped for futility.

Safety Stopping Analyses

Analysis of specific safety criteria will be performed to evaluate stopping enrollment for a specific cohort when there is at least 70% probability that the toxicity rate of any of the predefined safety events of interest (Protocol Section 3.3) in that cohort is above 25%. The safety stopping criteria will be applied separately within each cohort (AML or MDS) starting when at least 10 patients have completed the required follow-up period (28/24 weeks

for MDS/AML respectively) and applied continuously afterwards. Enrollment will continue unless the stopping boundary is crossed (Table 10 in Section 3.3 of the Protocol). Patients who have completed the required follow-up period or patients who have experienced any pre-defined safety events of interest within the required follow-up period will be included in the safety decision making. The same stopping criteria will be used for the AML and MDS cohorts; however, the two cohorts will be analyzed independently.

Final Analysis

The timing of the final analysis is determined by the expansion component of the study. The final analyses for MDS cohorts will be performed after all patients in the expansion MDS cohort have been followed for at least 28 weeks (to allow for confirmation of response per IWG 2006). The final analyses for the AML cohort will be performed after all patients in this cohort have been followed for at least 24 weeks.

Unblinding

The safety LIC and expansion component of the study are open-label and unblinding does not apply.

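### Section 3.3 has a sentence that stops study enrolment when either cohort misses its CR minimum, while the rest of the plan stops only the affected cohort

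*Protocol*

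**What the plan says.** Protocol 3.3 describes a Sponsor review of the CR rate within each expansion cohort, "to determine if the minimum number of responses are achieved to continue enrollment into that cohort". The next sentence gives the consequence: "If the minimum number of CRs in any group is not achieved, then study enrollment will stop for futility". The one after it keeps the study-level wording: "If the study is stopped for futility, patients on active treatment that are deriving clinical benefit will continue on study treatment".

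The tables in the same section are specific to a cohort. Table 8 is headed "Stop expansion MDS enrollment if there are this many responses total" and Table 9 "Stop expansion AML enrollment if there are this many responses total".

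Protocol 9.7.1 states the rule per cohort: "The decision rule is to stop enrollment for a specific expansion cohort". SAP 3 repeats that rule and adds the action: "The enrollment to the respective expansion cohort will be stopped". Both give the same worked example, in which 4 or fewer responders among 17 MDS patients stop enrolment to the MDS cohort. Both also open with a loose phrase about early stopping of the study for futility.

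**The concern.** Take 2 CRs in the first 10 evaluable MDS patients, which is a crossing under Table 8. Under 9.7.1, SAP 3 and the table heading, MDS enrolment closes and AML continues. Under the consequence sentence in 3.3, enrolment to the whole study closes. The same data lead to two different actions.

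The conflict sits in an operative stopping rule, and both 9.7.1 and the SAP point back to 3.3 for the rule or its boundaries. The study is open-label and the Sponsor does the CR review, so an unresolved ambiguity leaves room to choose a reading after seeing the data. The MDS boundary is much stricter than the AML boundary, so the main exposure is an MDS crossing that closes AML. The reverse is also possible.

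**Working it through.** **1. Reproduce the boundaries.** Inputs from Protocol 9.7.1: stop if Pr(E < S + 0.2) > 0.95. For MDS, E has prior Beta(1,6) and S is Beta(15,75). For AML, E has prior Beta(4,4) and S is Beta(23.5,97). After x CRs in n patients, E ~ Beta(a+x, b+n−x), and the probability is the integral over s of the S density times Pr(E < s + 0.2).

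- MDS: 2/10 gives 0.960 (stop) and 3/10 gives 0.882 (continue); 4/17 gives 0.950 (just above the cut-off, stop); 7/28 gives 0.951 (stop).
- AML: 0/10 gives 0.942 (no stop); 0/11 gives 0.957 (stop); 1/14 gives 0.951 (stop); 5/28 gives 0.959 (stop).

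Every row of Table 8 (n = 10 to 29) and Table 9 (n = 11 to 29) is reproduced. Each table uses only its own cohort's prior, control and data, so the calculation is cohort-specific and the boundaries are right.

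**2. Crossing probabilities.** Let f_n(k) be the probability of k CRs in n patients without an earlier stop. Then f_n(k) = (1−p)·f_{n−1}(k) + p·f_{n−1}(k−1), and at each n the mass at or below the boundary is removed and added to the stopping probability. There is a look after every evaluable patient up to n = 29.

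Scenario rates: 17% and 19.5% are the historical azacitidine CR rates in the Protocol; 36.7% is 15/90 + 0.2; 39.5% is 19.5% + 20 points; 25% is an intermediate assumption.

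- MDS crosses: 95.4% at 17%, 76.1% at 25%, 33.7% at 36.7%.
- AML crosses its own boundary: 2.9% at 39.5%, 59.5% at 19.5%.

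Much of the MDS probability falls at the first look. At 17%, Pr(X ≤ 2 of 10) = 0.83^10 + 10(0.17)(0.83^9) + 45(0.17²)(0.83^8) = 0.155 + 0.318 + 0.293 = 0.766. At 25% it is 0.526.

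**3. Literal reading, upper bound.** With independent cohorts and AML open throughout, Pr(AML closed) = 1 − (1−pM)(1−pA), where pA = 0.0285:

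- MDS at 36.7%: 1 − 0.663 × 0.9715 = 0.356
- MDS at 25%: 1 − 0.239 × 0.9715 = 0.768
- MDS at 17%: 1 − 0.0455 × 0.9715 = 0.956

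**4. Effect of the follow-up lag.** Enrolment continues during monitoring, and an MDS patient counts only after 28 weeks, which is 28 × 7/30.4375 = 6.44 months. The documents give no accrual rate, so assume r patients per month in each cohort with the same start. MDS look n occurs at n/r + 6.44 months, and AML is full at 30/r. The look can affect AML only if r < (30 − n)/6.44. For the first look, n = 10, the limit is 20/6.44 = 3.1 per month.

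| r per month | Last MDS look before AML fills | MDS crosses by then: true rate 17% / 25% / 36.7% |
|---|---|---|
| 1 | n = 23 | 92% / 71% / 32% |
| 2 | n = 17 | 89% / 67% / 30% |
| 3 | n = 10 | 77% / 53% / 23% |
| above 3.1 | none | 0 / 0 / 0 |

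**5. What AML would lose.** At the first MDS look AML has enrolled about 10 + 6.44r patients: 16 at r = 1 and 23 at r = 2. The maximum exact (Clopper-Pearson) 95% interval width, taken over all possible CR counts, is 0.374 at n = 30, which matches Protocol 9.1.2. It is 0.426 at n = 23 and 0.507 at n = 16.

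**The case against.** The best reply is that the intent is not in doubt. The preceding sentence in 3.3, both table headings, 9.7.1, SAP 3 and the worked example all stop one cohort. No document gives the disputed sentence precedence. The Sponsor that built the cohort-specific tables also does the review, and to act on the literal sentence it would have to override all of those places. The safety rule is likewise applied to each cohort independently. This stands: the practical risk is moderate, and the design itself is sound.

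It does not remove the point. Two consecutive sentences in 3.3 use study-level wording, and the introductory phrase recurs in 9.7.1 and SAP 3. The conflict is inside the Protocol, so the SAP alone cannot settle it.

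A reader might infer that the chance of losing AML really is 36% to 96%. The documents do not support that. Those figures need AML to be enrolling at every MDS look, and step 4 shows that the MDS contribution can be anything from nearly those values down to zero, depending on accrual.

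A reader might also infer that the AML primary objective would be lost. That does not follow either. Treated AML patients stay in the full analysis set, the CR rate and exact interval are still reported, Protocol 9.1.2 foresees 10 to 30 patients per cohort, and SAP 4.1 states no formal hypotheses. The loss is precision.

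**Conclusion.** The contradiction is real and should be corrected. Protocol 3.3 conflicts with itself, with 9.7.1 and with SAP 3 on the scope of a futility stop. The literal sentence gives the wrong action if followed, so it is more than a clerical slip. It is nonetheless a wording fault: the boundaries are correct and cohort-specific, and nothing in the documents supports a study-wide stop as the planned design.

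For an AML cohort at 39.5%, the chance of closure goes from 2.9% to at most about 36%, 77% or 96% at a true MDS rate of 36.7%, 25% or 17%. These bounds rest on independent cohorts, a look after each evaluable patient, the assumed true rates, and AML still open when MDS crosses. With equal accrual above about 3 per month per cohort, the MDS contribution is zero. In the other direction, an AML cohort at 19.5% crosses with probability 59.5% and, read literally, could close MDS, subject to the same kind of limit.

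**What to change.** In Protocol 3.3, replace the consequence sentence with: *If the minimum number of CRs in a cohort is not achieved, enrollment into that cohort will stop for futility; enrollment into the other cohort continues.* In the sentence after it, change *If the study is stopped* to *If a cohort is stopped*. In the opening sentence of Protocol 9.7.1 and of the futility paragraph in SAP 3, change *early stopping of the study* to *early stopping of the cohort*.

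The cost is three sentences in the next protocol amendment and one in the SAP. No boundary, prior, threshold or sample size changes.

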9.7.2. Safety Stopping Analyses

Analysis of specific safety criteria will be performed to evaluate stopping enrollment for a specific cohort when there is at least 70% probability that the toxicity rate of any of the pre-defined safety events of interest (Section 3.3) in that cohort is above 25%.

The safety stopping criteria will be applied within each cohort (AML or MDS) starting when at least 10 patients have completed the required follow-up period (28/24 weeks for MDS/AML respectively) and applied continuously afterwards. Enrollment will continue

unless the stopping boundary is crossed (Table 10 in Section 3.3). Patients who have completed the required follow-up period or patients who have experienced any pre-defined safety events of interest within the required follow-up period will be included in the safety decision making. The same stopping criteria will be used for the AML and MDS cohorts; however, the two cohorts will be analyzed independently.

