9.8. Data Monitoring Committee

This study will use an external data monitoring committee (EDMC). The EDMC will be responsible for ongoing monitoring of the safety of subjects in the study according to the charter. The recommendations made by the EDMC to alter the conduct of the study will be forwarded to Pfizer for final decision. Pfizer will forward such decisions, which may include summaries of aggregate analyses of endpoint events and of safety data that are not endpoints, to regulatory authorities, as appropriate. An EDMC will be convened to monitor safety in the study at least once per year.

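### The safety stopping rule starts at 10 completers but Table 10 counts completers or events; read literally, treatment-related deaths delay the rule meant to react to them

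*Protocol*

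**What the plan says.** Protocol Section 3.3 stops enrolment to a cohort on this criterion: "at least 70% probability that the toxicity rate of any of the below pre-defined safety events of interest in that cohort is above 25" per cent. One of the four events is "Treatment-related deaths that occur during study treatment through 28 days following the last dose of any study treatment".

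**When the rule starts.** Section 3.3 applies it "starting when at least 10 patients have completed the required follow-up period (28/24 weeks for MDS/AML respectively"). Section 9.7.2 repeats the condition ("starting when at least 10 patients have completed the required follow-up period"), and so does SAP Section 3.

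**Who is counted.** The first column of Table 10 carries a footnote. Besides patients who finished follow-up, "patients who have experienced any pre-defined safety events of interest within the required follow-up period will be counted". Section 9.7.2 agrees: "patients who have experienced any pre-defined safety events of interest within the required follow-up period will be included in the safety decision making". SAP Section 3 does too.

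**Boundaries.** Table 10 has no stopping for 1-9 patients, then at least 4 events for 10-12, 5 for 13-16, 6 for 17-20, 7 for 21-23, 8 for 24-27 and 9 for 28-30. A second footnote gives the prior: "A weak prior of Beta (0.5,0.5) was used in the calculation".

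**Around the rule.** Enrolment is continuous, to a maximum of 30 per cohort. On the monitoring committee, Section 9.8 says: "An EDMC will be convened to monitor safety in the study at least once per year".

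**The concern.** The start sentence and the footnote use different counts. The start sentence needs 10 patients who reached week 24 (AML) or week 28 (MDS). The footnote admits a patient on the day of an event.

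For a non-fatal event the difference is modest, because that patient can still complete follow-up and become one of the 10. For a treatment-related death within the window it is not. The death is an event and raises the Table 10 count, but that patient can never help to open the rule. The higher the rate of fatal toxicity, the more patients must be enrolled to produce 10 completers.

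Table 10 is the plan's only numeric stop for toxicity. If the start sentence governs, it is slowest when toxicity is early and fatal, and enrolment continues meanwhile. If the footnote governs, deaths bring the rule forward. A team applying the plan could defend either.

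**Working it through.** **1. Table 10 itself.** For n counted patients, the boundary is the smallest k with Pr(p > 0.25) ≥ 0.70 under Beta(0.5 + k, 0.5 + n − k). At n = 10, k = 3 gives 0.662 and k = 4 gives 0.862, so the boundary is 4. At n = 14, k = 4 gives 0.639 and k = 5 gives 0.825, so it is 5. All 21 values from n = 10 to n = 30 match the table. The boundaries are correct; the question is only when they start to apply.

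**2. The 10-12 row under the literal start.** If all events are deaths within the window, 10 completers plus k deaths make n = 10 + k. The row covers n ≤ 12, so k ≤ 2, but it needs 4 events. Four deaths give n = 14, where the boundary is 5. The first possible stop is 5 deaths at n = 15. The row can be crossed only if some events are non-fatal.

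**3. Enrolment when the rule opens, by hand.** Assume a 50% fatal event rate and no other losses. Ten completers then need 10 / 0.5 = 20 enrolled on average. While the last of them is followed, a further rate × W are enrolled, where W = 24 / 4.345 = 5.5 months (AML) or 28 / 4.345 = 6.4 months (MDS).
- At 0.5 per month: 20 + 2.8 = 22.8 (AML), 20 + 3.2 = 23.2 (MDS).
- At 2 per month: 20 + 11.0 = 31.0 and 20 + 12.8 = 32.8, both above the cap of 30.

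The chance that 30 patients never yield 10 completers is Pr(Bin(30, 0.5) ≤ 9) = 0.021.

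**4. Simulation.** Inputs from the documents: cap of 30, Table 10, 24/28 weeks. Assumptions: random accrual at the rate shown, 50% fatal events in roughly the first 7 weeks, no other losses, and a look at every completion or event. Mean number enrolled, AML / MDS:

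| Accrual per month | Start at 10 completers | Start at 10 counted |
|---|---|---|
| 0.5 | 23 / 23 | 12 / 12 |
| 1 | 25 / 26 | 13 / 14 |
| 2 | 28 / 29 | 16 / 17 |
| 3 | 30 / 30 | 19 / 20 |

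**5. Sensitivity to timing.** With deaths spread evenly over the whole window, the literal start changes by less than 0.5 patients. All 30 are then enrolled in about 10% / 10% of runs at 0.5 per month, 21% / 25% at 1, 58% / 72% at 2 and 90% / 96% at 3. The counted start rises to 12.6 / 12.8, 14.4 / 15.1, 18.3 / 19.8 and 22.4 / 24.4 at the four rates, still below the literal start.

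**6. Price of the earlier start.** Under the counted start, event patients enter at once while event-free patients wait 24 or 28 weeks, so early counts over-represent events. At an acceptable 10% event rate (AML, early events), the share of trials stopped rises from about 4% to 8% at 1 per month, and from about 7% to 14-16% at 2 per month.

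**The case against.** The best defence is that the footnote already settles the matter. The column it annotates is the one holding the 1-9 and 10-12 rows, and Section 9.7.2 and SAP Section 3 restate the counting rule in the same paragraph as the start sentence. That the literal start leaves the 10-12 row out of reach for deaths alone suggests that the authors meant 10 counted patients. This is a reasonable reading, but no sentence makes it the governing one, and the start condition is worded in terms of completion in all three places.

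A reader might infer more: that the rule cannot start, and that a cohort with 50% treatment-related deaths would enrol nearly all 30. The documents do not support that. It takes one of two available readings as settled, and it needs about 2 or more patients per month, an accrual rate the documents do not give. At 0.5 to 1 per month the literal start stops at about 23 to 26 on average.

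Nor is the rule the only safeguard. The monitoring committee has an ongoing remit, with yearly meetings as a minimum. An internal team reviews safety periodically, fatal SAEs are notified immediately, and the sponsor may terminate for safety. Half a cohort dying of treatment would not go unseen. These safeguards limit the consequence. They do not repair the rule, because none has a stated numeric trigger.

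**Conclusion.** The inconsistency is in the current text of both documents. Followed literally, it makes the stopping rule respond more slowly as fatal toxicity rises. In the 50% early-fatal case, the literal start enrols about 11 to 12 more patients on average than a start at 10 counted, at accrual rates from 0.5 to 2 per month (for AML, 23 against 12 at 0.5 and 28 against 16 at 2).

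Those sizes rest on a deliberately severe event rate, on assumed accrual and on no other losses; the documents give neither an accrual nor a loss rate. The direction does not depend on these assumptions: a death within the window can never add to the completers. Table 10 is correct, and the rule halts enrolment only. This is a should-fix: the passages must be reconciled, but the case does not call for a redesign of the safety monitoring.

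**What to change.** In Protocol Sections 3.3 and 9.7.2 and SAP Section 3, replace the start condition so that the rule applies once at least 10 patients in the cohort are counted as the Table 10 footnote defines: full follow-up reached, or a safety event of interest within it. Table 10 stays as it is, and its 10-12 row becomes usable for fatal events.

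The cost is a wording change in two documents and the higher stopping probability at acceptable toxicity shown in step 6. State that probability beside the rule, with the accrual assumed, so that those acting on an early crossing know that event patients reach the count first.

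Two further changes may suggest themselves, but I would not make them on this evidence. Counting event-free patients from Day 49 treats as event-free people still at risk of a qualifying death or confirmed liver injury. With 30% events spread over 24 weeks (AML, 2 per month), it stops early in 60% of trials, against 64% under the literal start and 83% with 10 counted. A hold at 4 events before 10 are counted would contradict the 1-9 row.
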